Please recheck your answers to make sure you have clearly marked each statement with an "x".

Thank you very much for your cooperation!

PBI-P – Patient Benefit Index, pruritus version**Treatment Benefits**

When the treatment began, you indicated in a questionnaire how important various goals were in the treatment of your skin disease.

Please mark each of the following statements according to the extent to which those treatment goals **were achieved**, indicating if the treatment has benefited you. If a statement did not apply to you, for example because you did not experience any pain, please mark "*did not apply to me*".

	The current treatment has helped me to ...	not at all	somewhat	moderately	quite	very	did not apply to me
1	...be free of pain						
2	...be free of itching						
3	...no longer have burning sensations on my skin						
4	...be healed of all skin defects						
5	...concentrate better						
6	...be less nervous						
7	...be able to wear all types of clothing						
8	...be able to bathe and shower normally						
9	...sleep better						
10	...feel less depressed						
11	...experience greater enjoyment of life						
12	...have no fear that the disease will get worse						
13	...lead a normal everyday life						
14	...be more productive in everyday life						
15	...be less of a burden to relatives and friends						
16	...engage in normal leisure activities						
17	...be able to lead a normal working life						
18	...be able to have more contact with other people						
19	...be more comfortable showing myself in public						
20	...be less burdened in my partnership						
21	...be able to have a normal sex life						
22	...be less dependent on doctor and clinic visits						
23	...need less time for daily treatment						
24	...have fewer out-of-pocket treatment expenses						
25	...have fewer side effects						
26	...find a clear diagnosis and therapy						

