Individual PBQ (‘Patient Benefit’ or ‘Benefit’) scores are in the SDTM data set QS. (QS.QSTESTCD.PBIP201 to QS.QSTESTCD.PBIP227).

1. Determine individual baseline PNQ scores.

2. Count PNQ scores, where individual score is from 1 to 4, as PNQ count.
3. Sum PNQ scores, where individual score is from 1 to 4, as PNQ sum.
4. Merge PBQ score at visit with corresponding baseline PNQ scores, creating item pairs. (e.g., merge PBIP101 with PBIP201) by subject-visit.
5. For each item pair, if both PNQ and PBQ score is 1 to 4, multiply PNQ*PBQ as calculated raw score.
6. Sum calculated raw scores as PBQ sum.
7. If PNQ count ≥ 21 , calculate and output PBI-P Global Score as (PBQ sum/PNQ sum).

However, for the score calculation, both “does/did not apply” and “question unanswered” will be treated as missing values. The global score will be calculated using only those items pairs (i.e., importance item and benefit item) for which the subject has given a response other than “does/did not apply” in both PNQ and PBQ. That is, importance items for which the corresponding benefit item has been rated as “does/did not apply” or “not at all” (or vice versa) will not be included in the sum of needs (i.e., the denominator in the algorithm).

The interpretation of data includes the distribution characteristics of PBI-P (e.g., mean and standard deviation) and the proportion of subjects with $PBI-P \geq 1$, $PBI-P \geq 2$, $PBI-P \geq 3$. Subjects with $PBI-P \geq 1$ are considered as having at least minimum patient-relevant treatment benefit (based on pilot studies).

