- Change in PAS as assessed by the percentage of subjects having a 1-category improvement in the percentage of healed lesions (item 5b) from baseline to Week 14 for the NAL ER treatment arm versus the placebo arm;
- Change in PAS as assessed by the percentage of subjects having a 1-category improvement in the percentage number of lesions (item 2) from baseline to Week 14 for the NAL ER treatment arm versus the placebo arm;
- Change in IGA-PN as assessed by the percentage of subjects having a 1-category improvement in activity from baseline to Week 14 for the NAL ER treatment arm versus the placebo arm;
- Change in IGA-PN as assessed by the percentage of subjects having a 1-category improvement in stage from baseline to Week 14 for the NAL ER treatment arm versus the placebo arm;
- The proportion of subjects with PBI-P ≥ 1 at Week 14 for the NAL ER treatment arm versus the placebo arm;
- The proportion of subjects with PBI-P ≥ 2 at Week 14 for the NAL ER treatment arm versus the placebo arm;
- The proportion of subjects with PBI-P ≥ 3 at Week 14 for the NAL ER treatment arm versus the placebo arm.

In addition, shift tables from baseline for improved ≥ 1 , no change, worsened ≥ 1 , and discontinued at Week 14 will be presented for PAS (item 5a), PAS (item 5b), PAS (item 2), IGA-PN for Activity, and IGA-PN for Stage.

Logistic Regression for Categorical Endpoints

The logistic regression model used for the primary endpoint will also be used for several secondary efficacy endpoints. Subjects with missing Week 14 measurement are treated as non-responders. Response rate, standard error, OR between the treatment groups, 95% confidence interval and p-values will be provided. The endpoints are:

- Change in PAS as assessed by the percentage of subjects having a 1-category improvement in the percentage of pruriginous lesions with excoriations/crusts (item 5a) from baseline to Week 14 for the NAL ER treatment arm versus the placebo arm;
- Change in IGA-PN as assessed by the percentage of subjects having a 1-category improvement in activity from baseline to Week 14 for the NAL ER treatment arm versus the placebo arm (95% CI only, with no p-value).

Sensitivity analysis for PAS (item 5a)

The sensitivity analysis to assess the impact of concomitant medications use for the primary endpoint will also be used for PAS (item 5a).

For open-label period visits, descriptive statistics will be displayed by treatment and overall for all secondary variables.

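### SAP 7.3.3 gives three different PBI-P denominators, and under one of them no computable score can fall below the responder cut of 1

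*SAP*

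**What the plan says.** SAP 7.3.3 builds the score in numbered steps and then qualifies them in a paragraph that begins with 'However'.

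- **Numerator (step 5):** "For each item pair, if both PNQ and PBQ score is 1 to 4, multiply PNQ*PBQ as calculated raw score". Step 6 adds these products.
- **Denominator in the steps (step 3):** "Sum PNQ scores, where individual score is from 1 to 4, as PNQ sum". The benefit answer plays no part.
- **Score (step 7):** when at least 21 needs are scored 1 to 4, "calculate and output PBI-P Global Score as (PBQ sum/PNQ sum".
- **Pair rule ('However' paragraph):** inapplicable and unanswered items are treated as missing. "The global score will be calculated using only those items pairs (i.e., importance item and benefit item", limited to pairs where neither answer is the inapplicable option.
- **'That is' sentence:** importance items whose benefit was rated inapplicable or 'not at all' are taken out. It closes with "or vice versa) will not be included in the sum of needs (i.e., the denominator in the algorithm".

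Subjects scoring 1 or more "are considered as having at least minimum patient-relevant treatment benefit". The proportion at or above 1 is the endpoint in protocol 11.1.2 and in the SAP's list of other secondary endpoints. SAP 8.6.3 adds the proportions at or above 2 and 3.

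**The concern.** The 'That is' sentence claims to restate the pair rule, but it changes it. 'Not at all' is a substantive answer on the Treatment Benefits form in protocol Appendix 2, where the inapplicable option is separate: "If a statement did not apply to you, for example because you did not experience any pain, please mark". Under the pair rule, a valued goal with no benefit pulls the score down, because its weight is in the denominator and it adds nothing to the numerator. Under the 'That is' sentence the goal disappears from both.

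The score then measures how large the benefit was where there was any, and no longer how much of what the subject wanted was achieved. The same answers can fall on opposite sides of the cut of 1 depending on which sentence the programmer follows, and the cuts of 2 and 3 move as well. Only the benefit half of the sentence matters: a need rated 'not at all' important has weight 0 under any rule.

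**Working it through.** The documents give no PBI-P value to reproduce, so the check applies the three rules to the same answers.

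**Inputs.** There are 27 items. Importance is coded 0 ('not at all') to 4 ('very') in SAP 7.3.3. The SAP states these codes for the needs form only. Coding a benefit of 'not at all' as 0 is inferred from them, from the 1-to-4 range in step 5, and from the SAP counting 0 and 5 as non-missing when answered benefits are counted.

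**Formulas.** Let w be importance and b benefit.

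- Numerator, all rules: sum of w×b over pairs with w and b both 1 to 4.
- Denominator, step 3: sum of w where w is 1 to 4.
- Denominator, pair rule: sum of w where w is 1 to 4 and b is answered 0 to 4.
- Denominator, 'That is' sentence: sum of w where w and b are both 1 to 4.

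**Illustrative subjects.** All 27 goals are 'very' important (w = 4), so the needs count is 27 and the step 7 condition of 21 is met.

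| Benefit answers | Numerator | Step 3 | Pair rule | 'That is' sentence |
|---|---|---|---|---|
| 13 'moderately', 14 'not at all' | 13×4×2 = 104 | 104/108 = 0.96 | 104/108 = 0.96 | 104/52 = 2.00 |
| 1 'quite', 26 'not at all' | 1×4×3 = 12 | 12/108 = 0.11 | 12/108 = 0.11 | 12/4 = 3.00 |
| 10 'moderately', 10 'not at all', 7 inapplicable | 10×4×2 = 80 | 80/108 = 0.74 | 80/80 = 1.00 | 80/40 = 2.00 |
| 27 'not at all' | 0 | 0/108 = 0 | 0/108 = 0 | 0/0 |

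In the first two rows the subject changes from below the cut of 1 to above it. In the second row one goal out of 27 is enough to meet all three cuts. In the third row the three rules give three different values.

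**Floor.** Under the 'That is' sentence every b that remains is at least 1, so sum(w×b) ≥ sum(w) and the ratio is at least 1 whenever it can be computed. Of 134,409 random answer sets scorable under all three rules, none fell below 1 under this sentence, against 68,829 under the pair rule. This checks the algebra and says nothing about rates in the trial.

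**General size.** With equal importance and all 27 benefits answered, let m be the mean benefit on goals with any benefit and s their share of the 27. Step 3 and the pair rule give m×s, and the 'That is' sentence gives m. To reach 1, the pair rule needs 27/m goals with some benefit, rounded up: 27, 14, 9 or 7 goals for m = 1, 2, 3 or 4. The 'That is' sentence needs one.

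**What the cut would mean under the 'That is' sentence.**

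- Percentages based on scored subjects: PBI-P ≥1 is 100% of them.
- Percentages based on the mITT population, with 0/0 counted as not meeting the cut: among subjects who pass the completeness conditions, PBI-P ≥1 means any benefit on at least one valued goal.

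**Which of these applies.** SAP 6.1 and 8.6.3 put the efficacy and secondary analyses on the mITT population. SAP 8.5.1.1 sends the remaining binary responder endpoints to logistic regression, and protocol 13.4.6.2 calls subjects with PBI-P ≥1 responders. SAP 8.6.3, however, reports PBI-P as counts and percentages and leaves it off the list for logistic regression. The rule "Subjects with missing Week 14 measurement are treated as non-responders" stands in that logistic regression text. A subject who answered every question and scores 0/0 is also not clearly a missing measurement.

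**The case against.** **The numbered steps are the algorithm.** SAP 7.3.3 introduces them that way, and step 3 produces no floor. This stands in part: the floor arises only if the 'That is' sentence overrides step 3. But the 'However' paragraph comes after the steps, reads as a qualification of them, and names the denominator explicitly. Dropping zero-benefit needs also matches the 1-to-4 condition in step 5, so it could well be coded. Following step 3 alone departs from the pair rule too (0.74 against 1.00 in the third row).

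**The endpoint could still separate the arms.** A reader might infer that PBI-P ≥1 must be 100% in both arms. The documents do not support that. It requires scored subjects as the percentage base, and the SAP's general rule points to mITT, where subjects without a score could leave a difference between the arms. A reader might also infer that the SAP is silent on unscored subjects; it is better described as unclear, given SAP 8.5.1.1 and protocol 13.4.6.2.

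**The departure from the intended meaning cannot be fully tested.** The SAP attributes the cut of 1 to pilot studies that are not available here, and the instrument's own scoring instructions are not reproduced. That stands, and it is why the fix does not declare one rule correct.

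**It is probably a slip.** It may be. It is still the written rule, and correcting it takes a phrase.

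**Conclusion.** The inconsistency holds as written. SAP 7.3.3 gives three denominators, and the choice can change responder status: 0.96 against 2.00, 0.11 against 3.00, or 0 against no score. If the 'That is' sentence governs, the floor of 1 is a matter of algebra for any data. The scores assume that a benefit of 'not at all' is coded 0. The answer patterns are illustrative, and the documents do not show how often such patterns occur, so no effect on the reported proportions can be estimated.

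The consequence is limited. PBI-P is an 'other' secondary endpoint, outside the test sequence in protocol 13.4.6.3 and last of nine in the ranking in SAP 8.6. The primary endpoint does not use it. The SAP should be corrected, but nothing here bears on the trial's main conclusion.

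A reader might also see a contradiction between the two completeness conditions in SAP 7.3.3. One accepts 21 of 27 valid answers on each form, with inapplicable answers counted. Steps 2 and 7 require 21 needs scored 1 to 4. Both can be applied together, so this is an alignment point only: a subject with 20 needs rated 'very' important and 7 inapplicable passes the first and is unscored under the second.

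**What to change.** - State one denominator rule, check it against the instrument's scoring instructions, and use it in step 3, the pair rule and the 'That is' sentence.
- If the pair rule is intended, delete the reference to 'not at all' for the benefit item in the 'That is' sentence, and restrict the step 3 sum to pairs with importance 1 to 4 and a benefit answered 0 to 4.
- State that subjects without a computable score stay in the mITT base, and how they count in the proportions at or above 1, 2 and 3.
- State the benefit-form codes explicitly, including 0 for 'not at all' if that is meant.
- Minor: align the count in steps 2 and 7 with the completeness rule of 21 valid answers out of 27.

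The cost is SAP wording and derivation code. No new data are needed.

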7.3.4. Prurigo Activity Score (PAS)

The PAS consists of 5 quantitative and qualitative measurements related to the examination of the skin: Type; number; distribution; quantitative number of lesions in a representative body part; and activity. Prurigo lesion activity is recorded as a stage (0 to 4), based on the percentage of overall lesions with the relevant characteristic.

Three types of PAS responders are defined, one for each of the following items: Prurigenous lesions with excoriations/crusts (item 5a); Healed lesions (item 5b); Number of lesions (item 2). For each of these, a responder is defined as a subject who has at least 1-category improvement in the relevant item from baseline to Week 14. For all three, a patient who does not have Week 14 measurement is a non-responder.

7.3.5. Investigator Global Assessment – Prurigo Nodularis (IGA-PN).

The IGA-PN collects an Investigator Global Assessment of the status of the PN skin lesions. The IGA-PN uses a 5-category scale (scoring 0 to 4) for assessing the status of 2 aspects of the disease: The Activity (amount of excoriation and crusting associated with the prurigo lesions), and the Stage (the quantitative presence and proportion of flattening of the lesions). An IGA-PN responder for Activity or Stage is defined as a subject who has at least 1-category improvement in the respective score from baseline to Week 14.

7.3.6. Sleep Scale

There is no assessment scale that is targeted specifically to evaluate sleep in the PN population. The Patient Reported Outcomes Measurement Information System (PROMIS) Sleep Disturbance Short Form 8a questionnaire has been developed as a general tool for assessing sleep in the context of clinical trials. It consists of 8 open-ended statements about the subject's sleep over the past 7 days, with 5 options for completing the statement. There is 1 broad sleep quality question with options for completing with: "very poor", "poor", "fair", "good", and "very good". The remaining 7 questions can be answered with: "not at all", "a little bit", "somewhat", "quite a bit", and "very much". The sleep scale score is estimated per algorithm below.

Each question usually has five response options ranging in value from one to five. To find the total raw score for a short form with all questions answered, sum the values of the response to each question and use [Table 1](#) in the Appendix to translate the total raw score into a T-score for each participant. The 95% confidence interval around the observed score is estimated as (T-score \pm (1.96*SE)).

7.4. Handling of missing data and outliers

7.4.1. Missing data analysis methods

For the primary efficacy endpoint, missing values at week 14 will be set to missing. The data will be analysed using the mixed model technique. The analysis assumes that the missing data is missing at random (MAR). Thus, it provides an unbiased estimate of the treatment effect that would have been observed had all subjects continued on treatment until Week 14. It therefore assumes that the response for withdrawn subjects will follow the trajectory of the respective treatment after discontinuation. In order to assess the robustness of the results to the MAR assumption, a sensitivity analysis will be conducted under

the assumption that the data is missing not at random (MNAR). The details of this analysis are described in

For the change from baseline in ItchyQoL and PROMIS, all observed data up to and including Week 14 will be used without using imputation methods for missing data. However, in sensitivity analyses, two multiple imputation (MI) methods will be used: Control based multiple Imputation and Tipping Point Analysis approaches

